### **SAMPLE SIZE**

To power our main patient outcomes, we planned to recruit 324 patients. With a conservative sample retention rate of 80%, we estimated a final sample size of approximately 260 patients at the 12 month follow-up, which would provide power of .80 or higher for the proposed analyses. We surpassed our enrollment goal and our final sample size was 376. With a 90% retention rate, our final sample size of patients at the 12 month follow up was 342, allowing sufficient sample to power to test all research hypotheses.

We illustrate power calculations for hypothesis testing based on our original proposed estimates, using worst case scenarios for each type of model used in the research aims, and assuming a Type 1 error rate of  $\alpha=.05$ . As an example of a continuous outcome, we consider the difference in activation scores between the Patient Activation (PA) + Usual Care (UC) and UC only groups. The cross-sectional analyses modeled by multivariate regression analyses will have a power of .80 to detect a conventionally small effect size of 0.07 with 12 independent covariates including the treatment group indicator, with a sample size of 260. We then examine the longitudinal analyses modeled by linear mixed-effects models. Assuming the worst case scenario of a correlation between the three repeated measures (baseline, 6 and 12 month questionnaires) to be 0.3 (analyses of prior studies indicate correlations of  $< 0.3$ ), the power to detect a 24% difference in standard deviation units will be .80 with a sample size of 230. As an example of power calculation for a binary response, we present statistical power for the likelihood of portal use between the PA+UC and UC groups. We will first examine the cross-sectional analyses modeled by multivariate logistic regression models. Based on results from an internally funded pilot study of complex patients, we expect an overall rate of portal use of 61%. The test of significance for an odds ratio of 2.5 for the coefficient of the indicator variable for treatment group (=1 if PA+UC, 0=UC), will have a power of .80 with a sample size of 166. In longitudinal analyses modeled by mixed-effects logistic models, using 3 repeated measures, for a worst case correlation of 30% between successive measurements, we will be able to detect a 12% difference between the PA+UC and UC groups with a power of .80 and sample size of 126 patients in each arm ( $n=252$ ). Given that our final sample size exceeded our original estimate, we have adequate power to examine main study questions.

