**[name], Data Analyst**. [name] primary responsibilities on the study were compiling final study results, and drafting methods and results for final research report and manuscripts. She cleaned survey data, retrieved relevant data from EHR and compiled final data tables. She created summary statistics for outcome variables, and compared differences between treatment groups on outcome measures at 6 and 12 months. She ran cross-sectional multivariate models to examine relationships between the outcomes and the two treatment arms at the 6-month and 12-month follow-ups, and used a repeated measures mixed effects framework to examine differences in outcomes by treatment arm over time.

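### The .80 power offered for the activation difference between arms fits a joint test of all 12 covariates, not the test of the treatment coefficient

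*Protocol*

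**What the plan says.** The SAMPLE SIZE section of the Protocol plans for about 260 patients at 12 months, "which would provide power of .80 or higher for the proposed analyses". It then illustrates power "using worst case scenarios for each type of model used in the research aims, and assuming a Type 1 error rate of" .05. Sidedness is not stated.

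The continuous example opens with the arm comparison: "we consider the difference in activation scores between the Patient Activation (PA) + Usual Care (UC) and UC only groups". The sentence that follows says the cross-sectional multivariate regression at N=260 has "power of .80 to detect a conventionally small effect size of 0.07 with 12 independent covariates including the treatment group indicator". The metric in which 0.07 is measured is not given, nor is the hypothesis being tested.

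The binary cross-sectional example in the same paragraph is explicit on the second point: "The test of significance for an odds ratio of 2.5 for the coefficient of the indicator variable for treatment group".

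The cross-sectional models were used. The data analyst's entry in the research team section records: "She ran cross-sectional multivariate models to examine relationships between the outcomes and the two treatment arms" at the 6-month and 12-month follow-ups.

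**The concern.** The difference between two arms is a single contrast, tested by one coefficient with 1 degree of freedom. The combination of 0.07, 12 covariates and N=260 looks instead like the input to an overall regression F test, which asks whether the 12 covariates together explain any variance in the outcome. The two tests answer different questions. The overall test can have high power because baseline covariates predict activation, whether or not the intervention does anything.

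If that is where .80 comes from, the sentence does not say what difference between PA+UC and UC the cross-sectional analysis could detect. A reader who takes 0.07 as the detectable arm difference is misinformed. Reading it as a standardised mean difference would suggest that the trial could find a 0.07 SD effect with power .80.

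**Working it through.** **Inputs from the SAMPLE SIZE section.** N = 260; 12 covariates including treatment; effect size 0.07; alpha .05; stated power .80. (324 recruited × 0.80 retention = 259.2, given as about 260.)

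**Assumptions.** The metric is not stated, so five are tried. Sidedness is not stated, so both are shown for the 1-df test. Allocation is taken as 1:1, in line with the 126 per arm in the longitudinal binary example; it is used to convert between f² and a standardised mean difference.

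**Method.** Noncentral F with noncentrality λ = f² × N, numerator df u (12 for the joint test, 1 for treatment) and denominator df v = 260 − 12 − 1 = 247. One-sided 1-df power uses the noncentral t.

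**Step 1: reproduce the stated figure.** With f² = 0.07, λ = 0.07 × 260 = 18.2. The joint test (u = 12) has power .803, and power .80 needs N = 259. This matches both stated numbers, so the arithmetic is sound for that test.

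**Step 2: try every usual metric on both tests.**

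| Reading of 0.07 | f² | Joint test, 12 df | Treatment, two-sided | Treatment, one-sided |
|---|---|---|---|---|
| f² | 0.07 | .803 | .989 | .995 |
| R² | 0.07/0.93 = 0.0753 | .838 | .993 | .997 |
| f | 0.07² = 0.0049 | .086 | .203 | .302 |
| r | 0.0049/0.9951 = 0.0049 | .086 | .203 | .303 |
| Standardised mean difference | 0.07²/4 = 0.001225 | .058 | .087 | .140 |

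No treatment-coefficient entry is near .80. With f² = 0.07 for treatment alone, power .80 would need N = 115 two-sided or 90 one-sided, not 260. With R² = 0.07 it would need 107 or 84.

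**Step 3: show that the joint figure is not evidence about treatment.** Let the other 11 covariates carry all of f² = 0.07 and set the treatment effect to zero. λ is still 18.2, so joint power is still .803. The treatment test then rejects 5% of the time.

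**Step 4: the figure for the stated comparison.** Solving for power .80 with u = 1, v = 247:

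- Two-sided: partial f² = 0.0304. Difference between arms at 1:1 = 2√0.0304 = 0.349 residual SD.
- One-sided: partial f² = 0.0239. Difference = 2√0.0239 = 0.309 residual SD.

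A 40:60 split would change these only to 0.356 and 0.316. In total SD, multiply by √(1 − R²), where R² is the variance explained by the other covariates. For an assumed R² of 0, .2 and .5 this gives 0.349, 0.312 and 0.247 two-sided, and 0.309, 0.277 and 0.219 one-sided.

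For comparison, f² = 0.07 for treatment alone would be 2√0.07 = 0.53 residual SD.

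**The case against.** The strongest reply is that nothing is miscalculated. The sentence attaches its power to a regression with 12 covariates and never says the .80 is for the treatment coefficient, so it may be a correct overall-model calculation with a loose introduction. The joint reading is also inferred. A joint test with 11 numerator df comes fairly close (.820, N 251). The matching metric errs on the cautious side: if f² = 0.07 were due to treatment alone, power would be .989. Finally, the consequences are small. The main longitudinal analysis has its own power statement in SD units, and 342 patients rather than 260 were followed to 12 months, which brings the two-sided detectable difference to about 0.30 residual SD (partial f² = 0.0231; 2√0.0231 = 0.304).

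Much of this stands. The arithmetic is right for the joint test, the metric is inferred, and no shortage of power follows. But the example is introduced as the difference between arms, and no tried metric or sidedness makes .80 the power of that comparison. The 11-df variant is still a joint test. The other power statements and the larger final sample do not correct the sentence.

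**Conclusion.** The point holds. The stated .80 is attached to a comparison it does not describe. It matches the joint 12-df test at f² = 0.07, while the treatment coefficient gives about .99 if 0.07 is f² or R², and .30 or less if it is f, r or a standardised mean difference. The sentence therefore does not give the arm difference detectable in the cross-sectional models. At N=260 with power .80 that difference is 0.35 residual SD two-sided or 0.31 one-sided, assuming 1:1 allocation and 12 covariates including treatment.

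The conclusion that .80 is not the treatment test's power does not depend on which metric was meant. The harm is confined to one reported planning figure. It does not show that 260 was too few, and it concerns only the continuous cross-sectional example.

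**What to change.** Restate the sentence for the treatment coefficient, naming the metric, the test and the sidedness actually used. For example: at N=260 with 12 covariates including treatment, alpha .05 [two-sided / one-sided] and 1:1 allocation, the test of the treatment coefficient has power .80 at partial f² = [0.030 / 0.024], that is, [0.35 / 0.31] residual SD between arms. The description of 0.07 as conventionally small is deleted with the old figure.

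If the joint 12-df test was intended, say so, and do not introduce it as power for the difference between arms.

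Cost: one planning sentence. Sample size and analysis are unchanged.

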### **AIMS**

**Aim 1:** Refine and finalize a patient-driven intervention curriculum and patient-centered outcomes, developed with a stakeholder group.

**Aim 2:** Compare the effectiveness of Patient Activation + Usual Care (PA+UC) versus Usual Care (UC) on patient-centered outcomes.

Will patients in the PA+UC arm:

- a. Have greater improvement in patient activation, patient satisfaction, pain and function scores, quality of life and provider communication over time?
- b. Be more likely to engage in self-management strategies?
- c. Be more likely to actively use primary care, and decrease use of acute care services?

**Aim 3:** To compare the effectiveness of PA+UC versus UC on prescription opioid use. Will patients in the PA+UC arm be more likely to reach their goal for prescription opioid use and/or decrease their use over time?

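### The longitudinal power of .80 at N=230 fits a one-sided test; on the two-sided convention of the binary figure beside it, power is .70

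*Protocol*

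**What the plan says.** In SAMPLE SIZE the power paragraph opens by "assuming a Type 1 error rate of" .05 and does not say whether tests are one- or two-sided. Its continuous example is the arm difference in activation scores. The longitudinal version runs: "Assuming the worst case scenario of a correlation between the three repeated measures (baseline, 6 and 12 month questionnaires) to be 0.3", with prior-study correlations reported as below 0.3, "the power to detect a 24% difference in standard deviation units will be .80 with a sample size of 230". A longitudinal binary example follows under the same alpha: three measures, correlation 30%, a 12-point difference in portal use, 126 patients per arm, power .80. The expected overall rate of portal use is given as 61%.

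Three statements build on these figures. About 260 patients at 12 months is a number "which would provide power of .80 or higher for the proposed analyses". The 342 patients actually followed to 12 months are described as "allowing sufficient sample to power to test all research hypotheses". The paragraph closes: "Given that our final sample size exceeded our original estimate, we have adequate power to examine main study questions".

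Aim 2a asks whether the intervention arm will "Have greater improvement in patient activation, patient satisfaction, pain and function scores, quality of life and provider communication over time". The data analyst's entry under RESEARCH TEAM says the analyst "used a repeated measures mixed effects framework to examine differences in outcomes by treatment arm over time". Neither place fixes the contrast.

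**The concern.** One unqualified alpha appears to have been used in two ways within one paragraph. If so, the power printed for the main type of outcome is about ten points too high on the convention of its neighbour, and the planned 260 did not clearly give .80 either.

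The contrast that fits best also gives the baseline survey a share of the treatment effect. That survey is completed at the consent visit, before any group session, so it cannot show an effect.

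The sentences about adequate power rest on this figure. Whether they hold at 342 depends on which longitudinal contrast is tested, and someone interpreting a null result needs to know what size of effect it excludes.

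**Working it through.** **Inputs.** From SAMPLE SIZE: difference 0.24 SD, three measures, rho 0.3, alpha .05, N=230 (read as the total), planned 260 of 324, achieved 342 of 376. Assumed: equal arms, one common correlation, no covariates, complete cases unless stated.

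**Formula.** With F the variance of a patient's contrast in SD² units, the standard error of the arm difference is sqrt(4F/N), and power = Φ(0.24/sqrt(4F/N) − z), with z = 1.645 one-sided or 1.960 two-sided.

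**1. The printed figure.** For the average of three measures, F = (1 + 2×0.3)/3 = .533. At N=230 the standard error is sqrt(4×.533/230) = .0963, and 0.24/.0963 = 2.492.
- One-sided: Φ(2.492 − 1.645) = .802. Patients per arm for .80: 2×.533×6.183/.0576 = 114.5, about 230 in total. This matches.
- Two-sided: Φ(2.492 − 1.960) = .703. Patients per arm for .80: 2×.533×7.849/.0576 = 145.3, or 292 in total.

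With serially decaying (AR(1)) correlation the two-sided power is .742. Reading 230 as per arm (460 in total, more than the 324 planned) gives no two-sided value within two points of .80 either. One one-sided value there comes close, .807 for mean follow-up minus baseline.

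**2. The neighbouring binary figure.** Take 61% as the lower rate (an assumption), so 61% against 73%, with the same factor .533. Per arm: (.61×.39 + .73×.27)/.12² × 7.849 × .533 = 126 two-sided, against 100 with 6.183 one-sided. A pooled-variance formula gives 128 and 101. The printed number is 126. If 61% is instead the midpoint of the two rates, the pooled formula gives 138 and 109, and neither matches. The cross-sectional example (odds ratio 2.5, overall rate 61%, printed N=166) points the same way: 162 two-sided, 128 one-sided.

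**3. Other contrasts for 0.24 SD at rho 0.3.** The last three columns are two-sided.

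| Contrast | F | 230, one-sided | 230 | 260 | 342 |
|---|---|---|---|---|---|
| Three-measure average, (1+2ρ)/3 | .533 | .802 | .70 | .755 | .86 |
| Baseline-adjusted mean of 6 and 12 months, (1+ρ)/2 − ρ² | .56 | .784 | .68 | .73 | .84 |
| Unadjusted mean of 6 and 12 months, (1+ρ)/2 | .65 | .730 | .62 | .67 | .79 |
| Mean follow-up minus baseline, (1+ρ)/2 + 1 − 2ρ | 1.05 | .552 | .43 | .47 | .58 |
| 12 months minus baseline, 2(1−ρ) | 1.40 | .457 | .34 | .37 | .47 |

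**4. The planned 260.** The three-measure average reaches .80 in two ways. One is a correlation of at most about .22. The other is to credit the baseline values of the 324 − 260 = 64 expected dropouts: a complete patient contributes 3/(1 + 2×0.3) = 1.875 units and a baseline-only patient 1, so 260×1.875 + 64 = 551.5, and Φ(0.24×sqrt(551.5/4) − 1.960) = .805. That second gain comes entirely from a measurement that cannot carry the effect. Baseline-only dropouts add nothing to the baseline-adjusted follow-up mean.

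**5. Worst-case correlation.** F for the three-measure average rises with rho, so 0.3 is its worst case if true values lie below 0.3. For the baseline-adjusted follow-up mean F barely moves (.54 at 0.1, .56 at 0.3). For change it falls as rho rises: at rho 0.1 the last two rows become 1.35 and 1.80, and power at 342 drops to .48 and .38.

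**6. Detectable difference at N=342**, two-sided, power .80: 2.80×sqrt(4F/342). Over rho 0.1 to 0.3 this is about 0.22 to 0.23 SD for the baseline-adjusted follow-up mean, 0.31 to 0.35 SD for mean follow-up minus baseline, and 0.36 to 0.41 SD for 12-month change.

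**The case against.** The strongest reply has four parts.

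- **The contrast and side are inferred.** The paragraph names neither. If 24% is rounded from 0.245, a one-sided test of the baseline-adjusted follow-up mean has power .799 at 230. A reader might therefore conclude too much from the match. It does not prove that baseline was averaged in, only that this fits best; and the alternative is also one-sided. The two-sided reading of the binary figure likewise depends on taking 61% as the lower rate.
- **The change figures test something the paragraph does not claim.** The example is a difference in scores, not in change, and a baseline-adjusted comparison is a legitimate answer to Aim 2a in a randomised trial. Read as a difference per visit, 0.24 SD would have two-sided power of .88 to .96 at 342 for rho 0 to 0.3, although at rho 0.3 and N=230 that reading gives .87, not .80. So a reader might infer that the trial was underpowered for Aim 2a, at .47 to .58. The Protocol does not support that without two further assumptions.
- **Covariates and lower correlations help.** If person-level covariates explained about 11% of the variance (an assumption), the three-measure average would reach .80 two-sided at 230. At rho 0.1 it would have .82. The text, however, states the figure at rho 0.3 and credits no covariates to it.
- **The figures are illustrations in a document written after follow-up, and sidedness can sit in an analysis plan.** This lowers the stakes. It does not remove the point, which is about a printed number and adequacy statements that the Protocol itself makes.

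**Conclusion.** The concern stands in limited form. At the stated inputs, .80 at N=230 is closely reproduced only by a one-sided test and conflicts with the two-sided convention that best explains the binary figure next to it. The two-sided value is ten points lower, and reaching .80 takes about 62 more patients (292 − 230).

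The achieved sample makes good the shortfall for the three-measure average and the baseline-adjusted mean of both follow-ups, so the closing claim of adequate power is right for those. It is too broad for all hypotheses: unadjusted change falls well short of .80 if 0.24 SD is meant as the difference in change. That last result is conditional and is not a finding that Aim 2a was underpowered.

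All of this assumes equal arms, a common correlation of 0.3, no covariate gain, 230 as the total, and 61% as the lower portal-use rate.

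**What to change.** 1. State that alpha .05 is two-sided.
2. Replace the figure at 230 with its two-sided value: power .70 at 230, or about 292 patients for .80. If the intended contrast is the baseline-adjusted follow-up mean, say so and give about 0.23 SD as detectable at N=342.
3. Limit the sentence on all research hypotheses, and the worst-case label on rho 0.3, to the three-measure average or the baseline-adjusted mean of both follow-ups.
4. If change from baseline is the tested contrast, give 0.31 to 0.41 SD as the detectable difference at N=342 over rho 0.1 to 0.3, covering mean follow-up minus baseline and 12-month change.

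The cost is a few reworded sentences, with no new patients, data or analyses. The downside is that the stated sensitivity becomes slightly less favourable.

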### **CONFIDENTIALITY**

In accordance with long-standing policy, all data collected as part of this study is being held in strict confidence. Only study staff has access to the data collected as part of the study, and all employees who come in contact with these records sign an agreement to maintain confidentiality. All study participant materials are stored electronically on a password protected, secure Kaiser Permanente Division of Research server. A Certificate of Confidentiality from NIH was obtained for the study.

All names are removed from research records; no identifying information is used in any report or publication that is produced from this study. Data will only be presented in the aggregate.

## **PARTICIPATION RECRUITMENT**

**Inclusion and Exclusion Criteria.** Our target population was all eligible adult primary care patients receiving care at the Santa Clara or San Jose Medical Centers, who were regularly taking prescription opioids at time of enrollment.

*Inclusion criteria.* (1) adult patients aged 18+ who received primary care at one of the study clinics and used prescription opioids for pain at least three days per week over the previous three months.

*Exclusion criteria.* Potential participants were excluded if they: (1) had any serious comorbidity other than their pain (e.g., terminal illness, active cancer, severe mental health issues such as psychosis), or any condition that would impair their ability to engage with the intervention; (2) were currently being treated in a pain clinic; (3) were in chemical dependency treatment; (4) had stopped or were planning to stop taking opioids before the intervention started; (5) had a relative or close friend participating in the study; or (6) did not read or understand English.

**Recruitment.** We used a multi-method approach to recruitment found to be very successful in previous studies. It included the following methods of making potential participants aware of the opportunity to participate in the study:

*Identification via EHR.* We identified potentially eligible patients through the EHR. With the approval of the patients' primary care physician, we sent eligible patients an IRB-approved recruitment letter with an invitation to participate. After 10 days, the research staff telephoned patients to determine if they were interested in participating in the study. Using an IRB-approved telephone screening script, the research staff screened and recruited eligible patients based on the study inclusion criteria.

*KPNC clinician referral.* Providers received instruction regarding the study and identification of eligible patients, as well as a referral script. Providers explained the study to potentially eligible patients, and provided a flyer to the patients so that they could contact study staff if interested.

Patients who were interested in the study, but not yet willing or interested in being contacted directly, were given a "Participant Information Sheet", which contained contact information for the Principal Investigator and research staff.

*Self-referral.* Fliers advertising the study were available in the clinic lobby. Interested patients could respond to the information on the study flier by calling a designated study phone number. The research

staff telephoned interested patients, using an IRB-approved telephone screening script, conducted a brief screening survey and invited eligible patients to participate.

**Informed consent and baseline appointment.** For patients who were eligible and agreed to participate, the research staff scheduled a one-hour, in-person appointment at the medical center at the patient's convenience. At the appointment, the research staff explained the study, invited the patient to participate, and obtained informed consent, using an IRB-approved recruiting script. Informed consent included access to patient medical records for research, including pharmacy and utilization of medical, mental health and chemical dependency services. The Research Associate answered all questions by the patient about the study, and reviewed the study consent form with the patients. If the participant stated that they understood the purpose of the study, and agreed to participate, the participant's signature was obtained. The research staff also clearly explained the HIPAA authorization form, and obtained the participant's signature.

After signing the consent form, the patient was asked to complete the online baseline survey, using a study laptop. The survey took about 45-60 minutes to complete.

**Randomization.** Randomization was conducted independently, using a block randomization approach and a SAS random-number generator. Assignments were pre-determined and placed in sealed opaque envelopes. As each eligible patient provided informed consent, the research staff opened an envelope to identify the treatment group to which the patient was assigned. Assignments were concealed from study staff until opened in front of patient.

Participants assigned to the intervention arm were required to attend their first session within 3 months of completing the baseline survey. In situations where this was difficult, participants were offered the option to re-do the baseline survey or forgo the group sessions and proceed with the remainder of the study (the 6 and 12 month follow up telephone interviews), which aligned with the planned intent-to-treat analysis of the study.

**Follow-up appointments.** Patients were interviewed by telephone at 6 and 12 months post intake. Trained DOR interviewers conducted follow up interviews (approximately 45 minutes) using standardized scripts and procedures. For patients who were difficult to reach by phone, we sent contact letters to let them know we were trying to reach them, and provided a telephone number to contact us. The Kaiser EHR was utilized for locating updated contact information. Multiple attempts were made to contact patients over 4-6 week time period.

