## **METHODS**

This was a randomized clinical trial in Adult Medicine, which compared a behavioral patient activation and pain self-management intervention to usual care for chronic pain patients using opioid pain medication.

**Study Site and Patients.** The study was located at the Santa Clara and San Jose Medical Centers of Kaiser Permanente Northern California, and led by a research team from the Kaiser Permanente Northern California Division of Research. The team included strong clinical research partnerships with the Chiefs

of Medicine at each site, [name] at Santa Clara and [name] at San Jose. The study sites were large primary care medical centers reflecting the diversity of the service area.

**Study Design.** The design was a pragmatic, randomized controlled trial with the patient as the unit of randomization. Eligible patients were those who used prescription opioids for a minimum of 3 days a week for the past 3+ months. We compared patient reported outcomes (see below) as well as health services use and prescription opioid use for those in the intervention arm to those who received usual care only (comparator group). We choose “usual care only” as the comparator group to best inform the intervention’s potential to enhance current practice. Usual care was determined by patients’ individual providers, according to practice guidelines related to specific conditions.

**Data Sources.** Patient-centered outcomes are reported from patient survey data at baseline, 6 and 12 months post recruitment. Pain is an individual experience, affected by individual factors, and patients and providers often have different definitions of treatment success. We assessed multiple domains to capture the patient experience. The EHR was the data source for patient clinical characteristics, patient portal use, prescription opioid use, and health services utilization.

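### Intervention-arm participants could re-do the baseline survey after allocation; if the later survey is used as baseline, the longitudinal survey contrasts start from a later measurement in one arm only

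*Protocol*

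**What the plan says.** All the procedural text is in the Protocol under PARTICIPATION RECRUITMENT.

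- **First survey, both arms.** "After signing the consent form, the patient was asked to complete the online baseline survey, using a study laptop".
- **Allocation.** The envelope was opened once the patient had consented. "Assignments were concealed from study staff until opened in front of patient".
- **Attendance rule, one arm.** "Participants assigned to the intervention arm were required to attend their first session within 3 months of completing the baseline survey".
- **Exception to that rule.** For patients who could not easily comply: "participants were offered the option to re-do the baseline survey or forgo the group sessions and proceed with the remainder of the study". That sentence ends with the remark "which aligned with the planned intent-to-treat analysis of the study".
- **Follow-up clock.** Under Follow-up appointments: "Patients were interviewed by telephone at 6 and 12 months post intake". Under METHODS, Data Sources, outcomes come from "patient survey data at baseline, 6 and 12 months post recruitment". Neither place mentions a re-done survey.

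On the analysis, Aim 2(a) asks whether the intervention arm improves more over time. SAMPLE SIZE treats the baseline, 6-month and 12-month questionnaires as three repeated measures with an assumed correlation of 0.3. The description of the data analyst's role gives two kinds of model: cross-sectional models at 6 and 12 months, and a repeated-measures mixed model for differences by arm over time.

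**The concern.** In a randomised comparison of change, the baseline should be measured in the same way and at the same point in both arms. Here one arm has a route to a second, later baseline, and that route opens only after assignment to that arm.

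The attendance rule is counted from the baseline survey, so re-doing the survey helps a late starter only if it resets that date. The natural reading is therefore that the second survey takes over as baseline. If the analysis follows that reading, pain, mood, activation or coping that moved between enrolment and the re-do is absorbed into the intervention arm's starting point, while the same movement in usual care counts as change. Improvement or regression to the mean before the re-do would shrink the apparent intervention gain. Worsening, or reporting altered by knowing the assignment, would enlarge it.

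The contrasts at stake are the longitudinal survey comparisons under Aim 2. Dispensing, utilisation and portal use from the EHR, and the cross-sectional 6- and 12-month comparisons, are largely unaffected unless their windows or baseline covariates are moved to the re-do date.

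**Working it through.** The Protocol states no figure for this point that could be reproduced. The check is therefore a reading of the timing, followed by an illustration of size.

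**Timing.** Let the survey be re-done r months after enrolment. The value of r is assumed; the Protocol gives no re-do dates. Usual care has 6 and 12 months on both counts below.

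| Baseline used | Follow-up clock | Interval affected | r = 2 | r = 3 | r = 4 |
|---|---|---|---|---|---|
| First survey | Intake | None | 6, 12 | 6, 12 | 6, 12 |
| Re-done survey | Intake | Baseline to interview: 6 − r, 12 − r | 4, 10 | 3, 9 | 2, 8 |
| Re-done survey | Restarted at re-do | Allocation to interview: 6 + r, 12 + r | 8, 14 | 9, 15 | 10, 16 |

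The first row removes the difference. The second follows the stated intake clock. The third is a possibility that the Protocol nowhere states.

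**Size, if the re-done survey replaced the first.** Inputs:

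- From SAMPLE SIZE: correlation 0.3; detectable difference 0.24 SD (used only as a yardstick); alpha 0.05. For 12-month numbers, "our final sample size of patients at the 12 month follow up was 342".
- Assumed: equal arms, so 342 / 2 = 171 per arm; a two-sided test; f, the share of the intervention arm that re-did the survey; and δ, the mean shift between the two surveys in SD units.

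Formulas:

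- Bias in unadjusted change = f × δ.
- Bias with baseline as a covariate = 0.3 × f × δ.
- SE of the change contrast = √(2 × (1 − 0.3)) × √(2/171) = 0.128.
- SE of the adjusted contrast = √(1 − 0.09) × √(2/171) = 0.103.
- Type I error = P(|Z + bias/SE| > 1.96).

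| f, δ | Unadjusted bias (share of 0.24) | Bias/SE | Type I error | Adjusted bias (share of 0.24) | Bias/SE | Type I error |
|---|---|---|---|---|---|---|
| 5%, 0.1 | 0.005 (2.1%) | 0.04 | 5.0% | 0.0015 (0.6%) | 0.01 | 5.0% |
| 10%, 0.2 | 0.020 (8.3%) | 0.16 | 5.3% | 0.006 (2.5%) | 0.06 | 5.0% |
| 20%, 0.2 | 0.040 (16.7%) | 0.31 | 6.1% | 0.012 (5.0%) | 0.12 | 5.2% |

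If 376 patients were split equally, 10% of the intervention arm is about 19 of 188. A larger assumed shift scales directly: f = 20% with δ = 0.5 gives 0.10 SD unadjusted (42% of 0.24) and 0.03 SD adjusted. No text in the Protocol supports or rules out any of these values of f and δ.

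**The case against.** **The harm depends on an unstated step.** The Protocol does not say that the second survey replaces the first, and an analysis plan not shown here may name the enrolment survey as baseline. This stands, and it makes the bias conditional. It does not remove the point, because the one-arm procedure is fixed in the Protocol itself and implies a reset baseline.

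**Timing need not be affected.** A reader might infer that follow-up timing is distorted however the clock is read. The documents do not support that: with the first survey and intake-based dates, nothing shifts.

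**The re-do may not be uniquely unblinded.** A reader might infer that usual care has a blinded baseline and the re-done surveys an unblinded one. Both the envelope and the first survey follow consent, and their order is not explicit. The first survey may itself have been answered with the arm known, in both arms. The secure asymmetry is the later re-measurement in one arm.

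**Usual care is not expressly barred from re-doing the survey.** That is correct. The one-arm reading follows from the scope of the attendance rule.

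**Intention-to-treat covers it.** It covers patients who skip sessions and stay in follow-up. It does not make a later baseline in one arm comparable with the enrolment baseline in the other.

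**The numbers are small and assumed.** This stands, and it decides the severity.

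**Conclusion.** The point holds as a minor one. The Protocol fixes a procedure by which some intervention-arm patients have a second, later baseline survey with their allocation known, and it describes no counterpart in usual care. If that survey is the analysis baseline, the longitudinal survey contrasts are not like for like, and one of two intervals (baseline to interview, or allocation to interview) differs between arms for those patients. If the first survey and intake dates are kept, the bias is zero.

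Size and direction cannot be derived, because the Protocol gives neither the number of re-dos, nor their dates, nor the shift between surveys. Under the main assumed range the effect is small: at most 0.04 SD unadjusted or 0.012 SD adjusted, with type I error at most about 6.1%. Those figures show scale only and are not estimates for this trial. A reader should not infer that the trial's conclusions are compromised; the documents give no basis for that.

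**What to change.** - Use the original enrolment survey as the analysis baseline for every randomised participant in both arms.
- Use re-done surveys only in a sensitivity analysis.
- Anchor EHR windows at randomisation in both arms.
- Report by arm how many participants re-did the survey and when, and the actual time from randomisation to each interview.

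No new data collection is needed, provided that the first surveys were kept, which the Protocol does not say. The downside is that for a few intervention patients the baseline lies further from the first session. Follow-up is over, so interview dates can no longer be changed. If first surveys were not kept, or interviews were re-dated from the second survey, report this as a limitation. If the envelope was opened before the first survey, the fix restores symmetry between arms but does not give a blinded baseline, and the report should state the order used.
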